Neonates and infants undergoing cardiac surgery are at high risk for perioperative bleeding and massive transfusion due to immature coagulation systems, cardiopulmonary bypass (CPB) effects (deep hypothermia, extreme hemodilution, large nonendothelialized surfaces) and complexity of surgery. The most common hemostatic derangement after CPB is an acute acquired hypofibrinogenemia, which compromises fibrin clot generation and platelet aggregation, resulting in increased bleeding and need for allogenic blood product transfusions. Recent studies suggest that qualitative and quantitative fibrinogen deficiencies may contribute to impaired hemostasis in neonates and infants (7). Using confocal microscopy, Brown et al demonstrated neonatal clot formation before and after cardiopulmonary bypass is more porous and less dense than clots from adults. However, the addition of adult fibrinogen was able to establish more effective clot formation in neonates (7). In conjunction with the decreased function of neonatal fibrinogen, the acute acquired hypofibrinogenemia after OHS contributes to impaired fibrin clot generation and platelet aggregation. Currently, fresh frozen plasma and cryoprecipitate are used to supplement fibrinogen in pediatric cardiac patients, thus increasing the allogenic transfusion exposures.

RiaSTAP (fibrinogen concentrate (FC)), an FDA-approved medication for congenital hypofibrinogenemia, is being used off-label for treatment of acute acquired hypofibrinogenemia associated with massive bleeding and CPB in adult and pediatric patients (8-10). Fibrinogen concentrate has many potential advantages for pediatric patients including 1) smaller volume to achieve target levels of fibrinogen, 2) decreased exposure to allogenic blood products, 3) decreased risk of infectious transmission, immunologic or allergic reactions, and 4) no required cross-matching or thawing process that makes it rapidly available for all patients. Recent studies found that FC was as effective as cryoprecipitate in reducing bleeding and transfusions for pediatric patients undergoing craniofacial and open-heart surgery (9,10). However, these studies did not specifically examine the neonatal and infant population, who are most vulnerable to the affects of hypofibrinogenemia, excessive bleeding and large transfusions associated with

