### Specific Aim #2:

Comparison of fibrinogen concentrate to cryoprecipitate as a safe and effective hemostatic agent:

By evaluating the laboratory values, transfusion requirements, and outcomes, we will examine the effectiveness of FC in reducing transfusion related risks, such as 1) length of mechanical ventilation time, 2) length of ICU stay, 3) length of hospital stay, 4) adverse events within seven days of surgery, 5) preoperative and post-operative coagulation laboratory values.

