## Specific Aim #2:

By evaluating the laboratory values, transfusion requirements, and short-term outcomes, we will examine the effectiveness of FC in post-bypass hemostasis. We will evaluate hematocrits, fibrinogen levels, and thrombelastogram values to determine if FC is at least as effective as the standard of care in post-bypass transfusion management. Secondly, we will evaluate secondary outcomes to determine if FC can decrease transfusion related risks such as increased mechanical ventilation, prolonged ICU/hospital stays, infection risks, and thrombosis.

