# **Data Safety Monitoring Plan**

A potential risk of this study is related to drug reactions including fever, chills, headache, allergic reactions, or thrombosis. This medication has been used extensively in Europe and as part of transfusion algorithms around the United States. Based on this data and the need to minimized transfusions in the infant population undergoing cardiac surgery with CPB, the FDA has granted an IND exemption for use of this medication in this randomized, control trial.

The study subjects will be reviewed on a case-by-case basis by the PIs at each institution and quarterly at a committee of experienced cardiac anesthesiologists not involved in the study for review of each study subject for potential adverse events and whether or not the event was related to the study.

A second risk of this study is patient confidentiality since protected health information is included in the study data. This risk will be minimized by only recording information absolutely necessary to fulfill the study's objectives. Information directly identifying patients will be excluded (names, addresses, telephone numbers, social security numbers, email addresses, and account numbers). A unique study number will identify the study subjects. The study information will be collected and stored in a password-protected database. Consents, along with the code linking a subject's identity to an assigned number, will be locked in the office of the principal investigator or designee.

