In secondary analyses, we used a Mann-Whitney U test to test whether the secondary outcomes measured continuously differed by arm. For categorical secondary outcomes, we used a Chi-squared test when the expected count in each cell was > 5, otherwise we used a Fisher's exact test. All secondary analyses were conducted on the subset of PP patients. Sensitivity analyses were performed for the secondary outcomes adjusting for site, complexity, weight, and CPB time. For continuous outcomes, we log-transformed the secondary outcomes then fit a linear regression model and for the outcome of any AE, we fit a logistic regression model.

Sample Size Justification: We designed our study to have 90% power to detect a reduction of two allogenic blood product transfusions when assuming that the mean number of units in patients receiving cryoprecipitate was 7 with a standard deviation of 2.2 units in both arms. Using a two-sample t-test and performing a two-sided test with an alpha = 0.05 we found that 27 patients per arm were needed. We assumed approximately 10% of patients would be missing their primary outcome and enrolled 30 patients per arm.

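### The SAP names only a pooled any-AE outcome, so thrombosis and infection, which the protocol says it will evaluate, have no identified analysis

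*SAP*

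**What the plan says.** **Protocol.** In the Significance section, Specific Aim #2 lists "adverse events within seven days of surgery" among its outcomes. In the methods, Specific Aim #2 says secondary outcomes will be used to see whether fibrinogen concentrate (FC) can lower transfusion-related risks, namely "increased mechanical ventilation, prolonged ICU/hospital stays, infection risks, and thrombosis". The Data Safety Monitoring Plan states: "A potential risk of this study is related to drug reactions including fever, chills, headache, allergic reactions, or thrombosis". Adverse Events Reporting gives the same list and describes these risks as comparable to those of cryoprecipitate. The Introduction and Background counts "decreased risk of infectious transmission, immunologic or allergic reactions" among the potential advantages of FC.

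**SAP.** In the secondary-outcomes section the general rule is: "For categorical secondary outcomes, we used a Chi-squared test when the expected count in each cell was > 5, otherwise we used a Fisher's exact". No outcomes are listed under it. The section then describes sensitivity analyses adjusted for site, complexity, weight and CPB time, and there the only adverse-event outcome appears: "for the outcome of any AE, we fit a logistic regression model". It also states: "All secondary analyses were conducted on the subset of PP patients". The SAP does not mention thrombosis, infection, allergic reaction, severity or seriousness.

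**The concern.** Two safety questions that the protocol poses, thrombosis and infection, are not carried into the SAP as outcomes. What is carried is one yes/no per infant. That composite scores a thrombosis the same as any other event, and a thrombosis in an infant who already has another event adds nothing to it. A difference confined to one event type is therefore diluted by every other type in the pool.

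The safety statement is what is at stake. The SAP title calls the product safe, and the Significance section frames Aim 2 as a comparison of safe and effective agents. A null result on any AE says little about thrombosis or infection in particular, yet it is the only adverse-event comparison the SAP identifies by name. The primary outcome, units transfused, is not affected.

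**Working it through.** **1. The plan's own figure.** The SAP's sample size concerns only the primary outcome. Inputs from the SAP: difference 2 units, SD 2.2, two-sided alpha 0.05, power 0.90. A two-sample t-test needs 26.43 per arm, rounded up to 27, and 27/0.9 = 30. Both stated figures reproduce. No adverse-event rate, power or sample size is stated in either document, so every event rate below is an assumption.

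**2. Which outcome has which analysis.**

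| Event | Protocol | SAP |
|---|---|---|
| Thrombosis | To be evaluated (Aim 2 methods); named risk (both safety sections) | Not named |
| Infection | To be evaluated (Aim 2 methods) | Not named |
| Allergic reaction | Named risk (both safety sections) | Not named |
| Any AE | Adverse events within seven days (Aim 2, Significance) | Adjusted logistic model |

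Neither document defines which events count as an AE. That the composite pools these types follows from the plain meaning of any AE, not from an explicit definition.

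**3. Dilution.** Let b be the proportion of infants with some other AE, equal in both arms, and t the proportion with thrombosis, assumed independent. Then

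any AE = 1 − (1 − b)(1 − t), and the difference between arms = (1 − b)(t_FC − t_cryo).

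With t = 5% on cryoprecipitate and 15% on FC:

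| b | Any AE, cryoprecipitate | Any AE, FC | Difference |
|---|---|---|---|
| 30% | 1 − 0.70 × 0.95 = 33.5% | 1 − 0.70 × 0.85 = 40.5% | 7 points |
| 50% | 1 − 0.50 × 0.95 = 52.5% | 1 − 0.50 × 0.85 = 57.5% | 5 points |
| 70% | 1 − 0.30 × 0.95 = 71.5% | 1 − 0.30 × 0.85 = 74.5% | 3 points |

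The factor (1 − b) is below 1 whenever other events occur, so under this model the direction of the dilution does not depend on the chosen rates. Its size does.

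**4. What separate reporting can and cannot deliver.** Exact power of a two-sided Fisher test at 0.05, 30 per arm, by enumerating both binomials:

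| Thrombosis, cryoprecipitate vs FC | Analysed alone | Inside any AE |
|---|---|---|
| 5% vs 15% | 0.09 | 0.05, 0.04, 0.03 at b = 30%, 50%, 70% |
| 5% vs 25% | 0.44 | 0.18, 0.10, 0.06 at b = 20%, 40%, 60% |

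Even alone, a threefold difference from 5% would rarely be detected. At 30 per arm, 0 versus 5 events gives Fisher p = 0.052 and 0 versus 6 gives p = 0.024.

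**5. Precision.** With no events among n infants, the two-sided exact 95% upper limit is 1 − 0.025^(1/n). For n = 30 it is 11.6%. For n = 27, used only to illustrate a smaller per-protocol arm because the documents do not give its size, it is 12.8%.

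**The case against.** - **The quoted sentence is a sensitivity analysis.** This stands. The main rule for categorical secondary outcomes is the chi-squared/Fisher sentence, which could cover single event types and suits sparse ones. A composite is also an understandable choice for a four-covariate logistic model in at most 60 infants. But the general rule lists no outcomes, so a reader cannot tell whether thrombosis or infection was ever to be tested.
- **Individual events are reviewed.** The protocol provides case-by-case review by the investigators and quarterly review by anesthesiologists outside the study. That protects individual patients, but it is not a comparison by arm.
- **Thirty per arm cannot settle thrombosis.** This stands, as the power figures show. The gain is in estimation and an honest safety statement, not in detection.

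A reader might infer more: that the plan lets a harm of FC be cancelled by a benefit. One can build such a case. With b = 50%, thrombosis 5% versus 15% and infection 20% versus 10%, any AE is 1 − 0.5 × 0.95 × 0.80 = 62.0% against 1 − 0.5 × 0.85 × 0.90 = 61.75%. But that result comes from choosing opposing effects of similar size. The protocol puts infection and thrombosis together as risks that FC might lower, and it calls the product risks comparable to those of cryoprecipitate, so thrombosis is not presented as peculiar to FC. The advantage claimed in the Introduction is infectious transmission, which does not support a halving of infection. Nor does either document say that most post-operative events are unrelated to the products, or that the safety conclusion would rest on the any-AE p-value.

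**Conclusion.** The concern holds as a gap between the documents. The protocol commits to evaluating infection and thrombosis, and the SAP identifies no analysis of either. A pooled outcome cannot answer those questions, and it shrinks a difference in one type by the factor (1 − b): from 10 points to 7, 5 or 3 in the illustration. That size rests on assumed rates, independence and equal background in the two arms. The documents do not show that a real harm was hidden or cancelled, and separate reporting would not give a powered test. The point should be addressed because it bears on the safety statement. It leaves the primary result untouched.

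**What to change.** In the SAP:

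1. Keep any AE as a descriptive summary.
2. List thrombosis, infection and allergic reaction within seven days of surgery as separate safety outcomes, and state what counts as each.
3. Report each by arm as number and percent of infants with an exact 95% confidence interval, and give the risk difference with its interval. State the denominator, since the SAP places secondary analyses in the per-protocol subset.
4. Base the safety statement on these intervals, not on an any-AE p-value, and say that they are descriptive.

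**Cost.** SAP wording and one table. The protocol says adverse events are recorded but not that they are coded by type, so some classification from the records may be needed. The intervals will be wide and the safety claim will read less favourably. Because the SAP already reports primary results, the table must be labelled as added later.

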for the first dose only. If a patient in either arm continues to have post-bypass bleeding, the anesthesiologist will use point of care testing and the transfusion algorithm to determine appropriate products for transfusion. Patients on the study arm will only receive the initial dose of FC; cryoprecipitate should be used for subsequent low fibrinogen levels.

Data regarding patient demographics, CPB variables, intraoperative and post-operative laboratory values, intraoperative and post-operative transfusion requirements, chest tube output, adverse events, length of ventilation time, ICU and hospital length of stay will be recorded and maintained in a HIPPA secure database.

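### The covariate-adjusted sensitivity models for secondary outcomes are poorly suited to 60 infants or fewer: unpenalised logistic regression for any AE, and a log transform with no rule for zeros (minor)

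*SAP*

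**What the plan says.** The SAP (Statistical Analysis for Secondary Outcomes) sets out two layers of analysis, both in the per-protocol set.

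- **Main tests.** For continuous outcomes, "we used a Mann-Whitney U test to test whether the secondary outcomes measured continuously differed by arm". For categorical outcomes, "we used a Chi-squared test when the expected count in each cell was > 5, otherwise we used a Fisher's exact test".
- **Adjusted models.** "Sensitivity analyses were performed for the secondary outcomes adjusting for site, complexity, weight, and CPB time". One sentence then gives both models. Its first half covers the continuous measures: "For continuous outcomes, we log-transformed the secondary outcomes then fit a linear regression model". Its second half turns to safety, where the wording is only that "for the outcome of any AE, we fit a logistic regression model".

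The SAP names no small-sample method for the logistic model and no rule for zeros before the log. It does not give the per-protocol size, the number of infants with an AE, the number of complexity levels or any adjusted odds ratio.

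The Protocol (Significance, Specific Aim #2) names ventilation time, ICU and hospital stay, AEs within seven days and coagulation laboratory values as outcomes, and says that transfusion requirements will be evaluated. Its Study Description adds, as recorded data, "intraoperative and post-operative transfusion requirements, chest tube output". The SAP does not list which of these count as secondary outcomes.

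**The concern.** A sensitivity analysis should be at least as dependable as the result it checks. Two features work against that here.

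First, maximum-likelihood logistic regression with few infants per coefficient tends to push a non-null odds ratio away from 1. When events are rare it may give no finite estimate at all. This model is the only covariate-adjusted AE estimate in the plan, and safety is part of Specific Aim #2.

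Second, the log transform applies to all continuous outcomes without exception. An infant extubated in the operating room could have a ventilation time of zero, and an infant with no post-operative transfusion has zero units. The log of zero does not exist, so the analyst must drop the infant, add a constant or change the model. The SAP does not say which. Dropping would remove the infants with the best values.

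**Working it through.** **Inputs from the documents.** Two sites (Protocol, Design). 60 infants enrolled, 30 per arm (SAP, Sample Size Justification). Covariates: site, complexity, weight and CPB time. Analysis set: per protocol, size not stated.

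**Assumed, because the documents do not say.** Per-protocol size 54 or 60; complexity with two or three levels; weight and CPB time entered linearly; AE rate 10-50%; true odds ratio 1, 2 or 3; modest to moderate covariate effects.

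**Step 1: the plan's own figure and where 54 comes from.** For a difference of 2, SD 2.2, two-sided alpha 0.05 and power 0.90, the normal approximation is n = 2 × (1.960 + 1.282)² × (2.2/2)² ≈ 25.4, so 26 per arm. The exact noncentral t gives power 0.895 at 26 and 0.906 at 27. The SAP's 27 is therefore reproduced, and 27/0.9 = 30 per arm. Taking 10% off 60 gives 54. That allowance is for a missing primary outcome, not for per-protocol exclusion, so 54 is only a working value. The documents give no figure for the AE model itself.

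**Step 2: parameters and sparsity.** Slopes: arm 1, site 1, complexity 1 (two levels) or 2 (three levels), weight 1, CPB time 1. That is 5 or 6 slopes, or 6 or 7 parameters with the intercept. The smaller outcome group is at most half the infants:

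- 60 infants: at most 30/5 = 6 per slope, or 30/6 = 5.
- 54 infants: at most 27/5 = 5.4 per slope, or 27/6 = 4.5.

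These are ceilings, reached only at an AE rate of 50%.

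**Step 3: bias with 54 infants.** 1,000 simulated trials per row, 1:1 allocation. The odds ratios shown are geometric means. The excess is (mean log OR − true log OR)/true log OR.

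| Parameters | AE rate | True OR | Maximum likelihood OR | Excess in log OR | No usable fit | Firth OR |
|---|---|---|---|---|---|---|
| 6 | 20% | 2 | 2.34 | 22.8% | 3.1% | 2.05 |
| 6 | 30% | 2 | 2.28 | 19.0% | 0.2% | 2.02 |
| 6 | 50% | 2 | 2.23 | 16.0% | 0% | 2.02 |
| 7 | 20% | 2 | 2.42 | 27.3% | 9.6% | 2.04 |
| 7 | 30% | 2 | 2.29 | 19.5% | 1.2% | 1.99 |
| 7 | 50% | 2 | 2.28 | 18.6% | 0.1% | 2.02 |
| 6 | 50% | 3 | 3.58 | 16.1% | 0% | 3.03 |
| 7 | 20% | 3 | 4.10 | 28.3% | 10.6% | 3.06 |

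The two rows for OR 3 are the extremes of the six run at 20-50%. At a true OR of 1 and the same AE rates, the maximum-likelihood OR is 0.96-1.03 and rejection is 3-6%. Interval coverage is 94-97% across all the 20-50% scenarios.

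**Step 4: dependence on 54 and on seven.** With 54 or 60 infants, 6 or 7 parameters, AE rates of 20-50% and a true OR of 2 (log OR 0.693), scoring both methods like for like:

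- Maximum likelihood: mean log OR 0.76-0.86. 0.76/0.693 = 1.10 and 0.86/0.693 = 1.24, so 10-24% too large.
- Firth: mean log OR 0.66-0.72, which is within about 5% of the truth. Root mean squared error is about 12-22% lower.

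Together with the 28% at OR 3 in step 3, the overall range is 10-28%.

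**Step 5: few events.** At a 10% AE rate, 54 infants yield about 5 events. In these runs 28-53% of fits separated or diverged; under other assumptions the share falls to about 8%. Among fits that succeeded at OR 2 or 3, the bias ran from −9% to +19%, so its direction is not fixed. Firth always gave an estimate but shrank somewhat: 1.81-1.98 for a true OR of 2, and 2.81 for 3.

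**Step 6: the log.** No figure can be computed, because the documents report no frequency of zeros. ICU stay, hospital stay and fibrinogen would normally be positive. Ventilation time and post-operative transfusion units can plausibly be zero.

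**The case against.** The strongest reply is that nothing important rests on these models. They are labelled sensitivity analyses. The main tests need no log, tolerate zeros, and switch to an exact test when expected counts are small. That stands, and it fixes the severity as minor.

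The inference from the logistic model is also sound where it matters most. Without an effect there is no material bias, and coverage is close to nominal at AE rates of 20-50%. The bias is small beside the noise as well: in a run with 54 infants, 7 parameters, a true OR of 2 and control-arm AE rates of 10-50%, it was 0.12-0.20 on the log scale against a root mean squared error of 0.76-1.10. This stands too. What remains is that Firth reduces both bias and error for no extra data.

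A reader might infer that a reported AE odds ratio is exaggerated. The documents give no such odds ratio and no AE count, so only an expected tendency can be claimed. A reader might also infer that infants were dropped, unequally by arm. No zero is reported, and the handling is not described: an offset may have been used. Nor does extending the point to negative blood-gas values hold, since base excess is named nowhere and blood gases appear only among routine draws. Chest tube output is recorded data, not a listed Aim 2 outcome.

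**Conclusion.** The point holds as a minor one, confined to the adjusted sensitivity analyses. The main secondary results do not depend on it.

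The sparsity of the AE model follows from the documented covariates and enrolment: at least 6 parameters, and at most 6 infants in the smaller outcome group per slope. The expected overstatement of a non-null log OR, about 10-28%, rests on an assumed 54-60 infants, AE rates of 20-50% and the simulated covariate effects. The chance of separation near a 10% AE rate, about 8-50%, depends heavily on assumptions. Seven parameters would require three complexity levels, which the documents do not state.

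The log-transform gap is real in the wording, but only for outcomes that can be zero. Its practical effect cannot be sized. The documents do not support saying that the models failed on the actual data or that they changed any conclusion.

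**What to change.** 1. Fit any AE with Firth-penalised logistic regression and profile-likelihood intervals, keeping the same covariates. The downside is slight shrinkage toward 1 when events are very few.
2. For secondary outcomes that can be zero (ventilation time, post-operative transfusion units), replace the log-linear model with proportional-odds regression on the raw value, with the same covariates. It is the regression counterpart of the Mann-Whitney test and drops no one. It reports an odds ratio instead of a percentage change, and it assumes proportional odds, which should be checked. It was not simulated here; the case for it is that it is defined at zero.
3. State the per-protocol size, the number of infants with an AE, the coding of complexity, and which outcomes are log-transformed.

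The cost is SAP wording and a re-run in standard software. No new data are needed, and the main tests stay as they are.
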